Appendix 4 The impact of hrHPV screening pilot on colposcopy services

Currently, NCSP data suggests approximately 1.5% of cervical cytology reports are high-grade (HSIL, ASCH, or AIS) while 5.5% of reports are low-grade (ASCUS {2%} or LSIL {3.5%}).

Patients with a high-grade cervical cytology are referred to colposcopy urgently (20 working days). Patients with a low-grade cervical cytology require a repeat cervical cytology or an hrHPV test prior to referral and are referred as semi-urgent to be seen within 26 weeks.

HPV tests are currently not recommended for patients under 30 years but are currently performed for over 90% of screened patients over 30 years with low grade cytology. On average, 61% of patients with LSIL cytology are hrHPV positive as are 23% of patients with ASCUS cytology.

According to the most recent NSCP report there are around 1600 referrals to colposcopy for high-grade abnormalities and 3200 referrals for low-grade abnormalities each year. Based on these figures, we estimate that approximately 1.5% of patients undergoing cytology are currently referred to colposcopy urgently and 3% are referred semi urgently. Thus, for 1000 patients screened with cytology, approximately 15 patients would be referred urgently and 30 patients referred semi-urgently.

Based on overseas studies, for primary hrHPV screening, we expect a hrHPV positivity rate of approximately 7% but this could vary from 5-10%. hrHPV positive samples will be divided into those that are positive for HPV 16 or 18 positive and those that are positive for other hrHPV genotypes. We have poor data on the proportions of these in the screening population in NZ, however, real-world data from Norway indicates we may expect about 25% of positives to be HPV 16 or 18.

Based on the Norwegian data, we can estimate that approximately 30% of patients with HPV 16 or 18 positive samples will have normal cervical cytology. For patients with other hrHPV positive samples, an estimated 45% will have a normal cervical cytology and 35% will have a low-grade cervical cytology.

Thus, if all patients with (a) HPV 16/18 positive samples and (b) with other hrHPV positive samples and high-grade cytology are referred urgently we might expect 26 per 1000 patients screened to be referred urgently (18 patients with HPV 16/18 and 8 with other hrHPV). In addition, if all patients with other hrHPV and low-grade cytology are referred semi-urgently to colposcopy, this would be an additional approximately 18 per 1000 patients screened.

The total number of patients referred in this instance will be similar whether based on hrHPV primary screening (44) or on cervical cytology primary screening.(45) However, the number of patients referred urgently would increase from 15 to 26 per 1000 patients screened. If patients with hrHPV 16/18 and normal cytology are referred semi-urgently this may reduce the number referred urgently to 21 per 1000 patients screened.

Therefore, within the context of this pilot study there we expect no appreciable increase in the number of colposcopy referrals in the first round of screening, however it may lead to a higher number of urgent referrals. In each service this is likely to number in the region of 11 patients over 6 months and as such is unlikely to have a significant impact on service provision.

Clearly these numbers are purely estimates, as we have little data from NZ with regard to hrHPV incidence by type. One of the principle aims of this study is to identify, for NZ patients, the relative proportions of hrHPV type and cytology results in order that estimates of colposcopy workloads can be made.

For the national roll out of primary hrHPV screening, the implication of these numbers are more significant. If patients with other hrHPV and low-grade cytology are not referred for colposcopy this will significantly reduce demand for non-urgent colposcopy but not alleviate the demand for urgent colposcopy. An additional cumulative colposcopy load will be created from patients who have persistent hrHPV infection with or without abnormal cytology therefore follow up protocols of this category of require careful monitoring.

Colposcopy management is to a large extent unaltered by hrHPV screening however some patients will present to colposcopy without cytology to guide the colposcopist and the risk of CIN2 or worse will vary by hrHPV type and cytology. Draft guidelines regarding management and follow up of patients referred to colposcopy have been written by the NCSP and will be available to treating colposcopists. In essence as per standard practice patients over 25 with a histologically confirmed high grade will be recommended to undergo treatment. Patients with low grade or normal cytology and no colposcopic evidence or histology of a high-grade abnormality will undergo a repeat hrHPV test (+/- cytology in 12 months). Patients with high grade cytology but no colposcopic evidence of a high-grade abnormality can be reviewed at an MDM if high grade cytology is confirmed treatment is recommended (particularly if type 3 TZ) or alternatively the patient should undergo repeat colposcopy cytology and hrHPV test in 6 months. These recommendations represent little material change from current management.

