Patients with a previous high-grade abnormality or glandular abnormality, and who have not completed test of cure are recommended to undergo cytology at the time of hrHPV testing. If cytology or hrHPV testing is abnormal the patient should be referred to colposcopy. If a patient has had a prior low-grade abnormality (and no high grade) or has completed a test of cure they can be managed as per patients undergoing routine screening. When reporting the test, the laboratory will have access to the prior screening history. If a cervical cytology test (test of cure) is indicated but has not been taken, this will form part of the report.

Handling of specimens

Specimens will be delivered to the participating practice or central study location or the practice in person or by return courier envelope. The specimens will be logged and then sent on to the participating laboratory by courier or other suitable delivery mechanism. In some circumstances if a home test has been performed the specimen will be delivered directly to the laboratory. In this case consent forms will be collected by the laboratory and returned to the study centre. It is recommended that samples are sent to the lab within 48 hours of being taken. Results are to be reported within 5 working days of being received by lab.

Clinical responsibility for cervical tests

hrHPV tests organised by practice staff will be the responsibility of that practitioner (cervical screener).

hrHPV tests organised by the central recall system will be deferred to the designated lead in the practice. A method of coordination between the practice and the central recall will be determined. The centralised recall will be responsible for ensuring the designated practice is aware of the test and

the result. Patients with a positive result will require a face to face or a telehealth appointment to discuss the result.

Test Results

Test results will be reported according to normal locality and service-based protocols. The report will be issued to the clinician responsible for the test. A copy of the report will also be provided to the central study coordinator.

hrHPV results may be reported as follows

- Unsatisfactory test
- hrHPV Negative
- hrHPV Positive
- HPV 16 and or 18 and or HPV other(non-16 non 18 types) (extended genotyping may be reported if available)

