Clinical override will upgrade the urgency of referral including patients with an abnormal appearing cervix, symptoms, are under-screened or who have perceived barriers will be referred to colposcopy urgently at the discretion of the cervical screener.

Colposcopy and pathology records will be sourced via the provider (with permission of the patient).

Patients with positive hrHPV may be referred to colposcopy in the absence of cytology triage as follows: Pacific and Māori patients, under-screened patients, and patients with HPV16/18.

As identified by the Māori Steering Committee, cervical cytology testing is a probable barrier for Māori patients

(https://www.heiahurumowai.org.nz/_files/ugd/b7edfc_621f3417d3b84349be2ed6372d479d30.pdf). It is particularly important to fully discuss the indications for cervical cytology with patients and to explain that they are able to opt for direct referral to colposcopy without cytology screening, if they would prefer it.

Previous cervical abnormality may also be an indication for referral in the presence of an abnormal hrHPV test.

Colposcopy

Colposcopy will be performed as per standard practice guidelines. Patients who have had no cytology in the last 3 months or normal cytology should have a cytology performed. If feasible at least 1 biopsy should be taken of any visible lesion or the cervical transformation zone. Treatment protocols will adhere to NCSP guidelines. Relevant colposcopy and treatment data will be retrieved to be included in the study dataset.

Patients who do not attend for recommended cytology or colposcopy

The management of these patients should be consistent with normal practice.

Non-attendance for colposcopy is associated with a risk of cancer and every effort should be made to ensure attendance. Where possible a medical practitioner should discuss this with the patient and make an individualised plan for their follow up. The NCSP will be notified.

Patients with hrHPV other following a self-test who decline cytology may be referred to colposcopy. If this is declined where possible a medical practitioner should discuss this with the patient and make an individualised plan for their follow up. The NCSP will be notified. Support to Screen services will be utilised as per normal practice.

Data management

A detailed Data Management Plan is available as a separate document.

All patient data are confidential, and for Māori patients, data are recognised as taonga.

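### Appendix 4's printed cytology split for other hrHPV gives 10.5 urgent referrals per 1000, not the 8 behind its 26 urgent and 44 total

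*Protocol*

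**What the plan says.** Appendix 4 builds its forecast per 1000 screened from these inputs:

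- Positivity: "we expect a hrHPV positivity rate of approximately 7% but this could vary from 5-10" per cent.
- Genotype: "we may expect about 25% of positives to be HPV 16 or 18".
- HPV 16/18 cytology: "approximately 30% of patients with HPV 16 or 18 positive samples will have normal cervical cytology".
- Other hrHPV cytology: "an estimated 45% will have a normal cervical cytology and 35% will have a low-grade cervical cytology".

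It then presents as a consequence that "we might expect 26 per 1000 patients screened to be referred urgently (18 patients with HPV 16/18 and 8 with other hrHPV"). It adds about 18 semi-urgent referrals (other hrHPV with low-grade cytology), for a total of 44 against 45 under cytology screening (15 urgent, 30 semi-urgent). If HPV 16/18 with normal cytology is semi-urgent, it gives 21 urgent. On the increase in urgent referrals it says: "In each service this is likely to number in the region of 11 patients over 6 months". From this it concludes that total referrals should not rise noticeably and that services should cope.

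Other sections bear on the count. Under Referral to colposcopy, HPV 16/18 with normal cytology is intermediate risk and semi-urgent, whereas the Appendix 6 legend makes every HPV 16 or 18 positive result urgent. Referral to colposcopy also says: "Patients with positive hrHPV may be referred to colposcopy in the absence of cytology triage as follows: Pacific and Māori patients, under-screened patients". The Test of Cure section says of patients with an earlier high-grade or glandular abnormality: "If cytology or hrHPV testing is abnormal the patient should be referred to colposcopy".

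**The concern.** The input shares and the resulting counts stand next to each other in Appendix 4, and the counts are worded as following from the shares. For other hrHPV they do not: the shares leave 20% for the only remaining group that is counted, while the 8 needs about 15%. The error carries into the 26, the 44, the 21 and the 11. Those figures are the stated grounds for saying that the pilot will not strain colposcopy services, and the Background names the impact on those services as an important focus of the study. The total also covers a narrower set of routes to colposcopy than the protocol allows, and the appendix does not say so.

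**Working it through.** **Inputs.** Positivity 7%, HPV 16/18 share 25%, HPV 16/18 with normal cytology 30%, other hrHPV 45% normal and 35% low-grade, baseline 15 urgent and 30 semi-urgent (all Appendix 4). About 1000 screened per service (Methods: at least 3000 people in 3 regions).

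**The plan's figures that reproduce.**
- Positives: 1000 × 0.07 = 70.
- HPV 16/18: 70 × 0.25 = 17.5 (printed 18).
- Other hrHPV: 70 − 17.5 = 52.5.
- Other hrHPV, low-grade: 52.5 × 0.35 = 18.4 (printed 18).
- The 11 is 26 − 15 at about 1000 screened per service.
- The 21 is 26 − 17.5 × 0.30 = 26 − 5.25 = 20.75.

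**The figure that does not.** Other hrHPV, remainder: 52.5 × (1 − 0.45 − 0.35) = 10.5 (printed 8). The 8 needs 15% (52.5 × 0.15 = 7.9), and the stated shares would then sum to only 95%.

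**Where the 8 may come from.** The Appendix 3 tables give, for other hrHPV, ASC-US 498, LSIL 225 and high-grade 294. A further row of 981 carries the same 9.4% CIN2+ risk that the Appendix 3 summary lists for other hrHPV with normal cytology. Taking the two tables as one cohort:
- Sum: 981 + 498 + 225 + 294 = 1998.
- Normal 981/1998 = 49.1%; low-grade 723/1998 = 36.2%; high-grade 294/1998 = 14.7%.
- Per 1000: high-grade 52.5 × 0.147 = 7.7; low-grade 52.5 × 0.362 = 19.0.
- Urgent 17.5 + 7.7 = 25.2; total 25.2 + 19.0 = 44.2.

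**Side by side, per 1000 at 7% positivity.**

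| | Printed | Printed split (45/35/20) | Appendix 3 split (49/36/15) |
|---|---|---|---|
| Other hrHPV, high-grade | 8 | 10.5 | 7.7 |
| Urgent, all HPV 16/18 urgent | 26 | 28.0 | 25.2 |
| Extra urgent over 15 | 11 | 13.0 | 10.2 |
| Urgent, HPV 16/18 with normal cytology semi-urgent | 21 | 22.75 | 20.0 |
| Extra urgent over 15 | 6 | 7.75 | 5.0 |
| Total | 44 | 46.4 | 44.2 |

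**Routes not counted.** Appendix 4 counts other hrHPV with normal cytology (52.5 × 0.45 = 23.6 per 1000) as no referrals. Some could reach colposcopy without cytology, but no uptake rate is given. As an illustration only, assume that every Māori and Pacific self-tester with other hrHPV goes direct. Take the national shares in Practice selection (16.5% + 8.1% = 24.6%, no overlap) and 60–70% self-testing (Statistical Considerations). The total then rises by 23.6 × 0.60 × 0.246 = 3.5 to 23.6 × 0.70 × 0.246 = 4.1 per 1000.

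**The case against.** The strongest case is that little turns on this. Correcting the split moves the total from 44 to 46 against 45. The stated positivity range of 5–10% alone moves urgent referrals from 20 to 40 per 1000 on the printed split. Appendix 4 calls its figures estimates and drives no sample size, endpoint or analysis. All of that stands, and it limits the weight of the point. It excuses uncertain inputs, but not a product that does not follow from the inputs printed beside it.

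Two stronger readings are tempting, and the documents support neither.

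- A reader might infer that the extra 11 urgent referrals per service is simply too low. That holds only if the printed split is right and all HPV 16/18 are urgent. If HPV 16/18 with normal cytology is semi-urgent, the same split gives 7.75, so 11 would be too high. If the Appendix 3 counts are the true source, the printed totals broadly stand. The 26 and 44 also follow the structure of the Appendix 6 rule.
- A reader might infer a much larger load by adding direct referrals, overrides and test-of-cure referrals. Direct referral is permitted rather than required, and override is at the screener's discretion. Appendix 3 recommends cytology triage for all hrHPV positives, with exceptions. No rates are given. Non-return for cytology, which the protocol treats as a real risk, lowers referrals. Test-of-cure referrals are not shown to be absent from the cytology baseline of 45. The net effect cannot be derived from the documents.

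**Conclusion.** The point holds as an internal contradiction. The printed 45%/35% split and the printed 8 cannot both stand. On the printed split, with the remainder taken as high-grade, 7% positivity, 25% HPV 16/18, all HPV 16/18 urgent and about 1000 screened per service, the figures are 10.5, 28 urgent, 46 total and 13 extra urgent per service. The differences are about 2 to 2.5 per 1000. The conclusion that total referrals will not rise noticeably is roughly unchanged at 7%.

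The documents do not settle which number is the slip, although the Appendix 3 counts point to the 45%. The direction of any error in the 11 depends on the unresolved conflict between Referral to colposcopy and Appendix 6. The 44-versus-45 comparison also leaves out routes that the protocol permits, of unknown size.

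**What to change.** In Appendix 4:

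1. Make the split and the figures agree. Either restate the split as about 49/36/15 and keep 8, 26 and 44, or keep 45/35, state the 20% high-grade share, and print 10.5, 28, 46, 23 (for 21) and 13 extra urgent per service. On the first route low-grade becomes 19.0, so show one decimal (17.5 + 7.7 + 19.0 = 44.2); the rounded rows would not add to 44.
2. Reconcile Referral to colposcopy with the Appendix 6 legend on the urgency of HPV 16/18 with normal cytology. Until then, give the extra urgent figure under both readings: about +10 to +13 if all are urgent, and about +6 to +8 if those with normal cytology are semi-urgent (+5 with unrounded Appendix 3 shares).
3. State that the total covers only cytology-triaged routes. It excludes discretionary direct referral, override and test-of-cure referrals, and it assumes that everyone returns for cytology. Any allowance for these should be labelled as an assumption.
4. Qualify the sentences on total referrals and on 11 patients per service to match.

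The cost is rewording and recalculation. Items 1, 3 and 4 change no patient numbers, procedures or analyses. Item 2 asks only that the two passages be made to agree.

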The study aims to include patients from a cross-section of demographic characteristics. To ensure representation from practices with a higher proportion of Māori and Pacific patients, from rural locations, and with higher levels of social deprivation, the demographic characteristics of each practice was investigated and categorised by the following variables:

- Rural location
- Urban location + higher proportion of women with a mixed/high socioeconomic index
- Urban location + higher proportion of women with a low socioeconomic index
- Proportion of Māori women enrolled at or higher than the overall proportion of Māori in the NZ population (16.5%)
- Proportion of Pacific women enrolled at or higher than the overall proportion of Pacific in the NZ population (8.1%)

In Whanganui, following discussion with iwi representatives, five practices were selected by the Whanganui Leadership Team which represent the 6 iwi in the region. Screening for cervical cancer using hrHPV testing is seen as significant opportunity to address existing and emerging inequality. This screening approach has the capacity to improve participation for Māori and other under-screened populations. The hrHPV pilot provides an opportunity for Māori patients and other under-screened patients to be included in community engagement with the research study. The development of a

locality leadership approach in Whanganui provides the opportunity for an integrated iwi, community and GP clinic approach for screening to develop. The Whanganui hrHPV study steering group has included GP clinics in the study that will reflect this approach and demonstrate an emerging integrated model of care.

The Whanganui population has a high representation of Māori women and rural practice. In order to provide a balance in demographics, as reported in the aims, in Capital & Coast and Canterbury, four practices from each region would be selected at random, but an additional practice in each region would be chosen at random from within practices with a higher than population level of eligible Pacific women enrolled. In all cases, if a selected practice does not consent, then another practice with a similar demographic profile will be randomly selected.

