In order to align with current NCSP practices, in terms of database requirements and automatic recall procedures, all patients in the clinician-taken sample group will have a cytology assessment of the sample they have already given, thus, do not need to return for a follow up cervical screen. The two groups, therefore, cannot be directly compared in terms of failure to return for follow up. In addition, as the clinician-taken and self-sample groups are self-selected they will be different and, hence, outcomes from the two groups will be recorded but cannot be directly compared.

Due to the relatively small size of this study and the unlikely outcome of a high-grade cervical abnormality, outcomes related to colposcopy referral will lack the power for stratification. However, the choice of screening method may usefully be able to be stratified.

Transfer of data and patient care to the NCSP.

The NCSPR will be informed of all patients participating in the study.

As the NCSPR is not currently able to manage the results of hrHPV screening this information will be overseen by the study team. The study team will act in place of the NCSPR to provide reminders to the practices when patients are overdue further investigations or repeat testing and to ensure management recommendations are correct. Following colposcopy or on completion of the study when the NCSPR is able to manage these patients' information they will be referred back to the NCSPR

Results of all cytology tests and hrHPV tests and colposcopy records will automatically be referred to the NCSPR. The study team will follow all patients to the end of the study to ensure patients who require colposcopy have been seen.

At completion of the study enrolled patients will fall under the following categories.

- Normal screen, next routine screen to be performed at the normal screening interval (5 years)
- Normal screen but because of previous abnormality follow up recommended in 12 months
- Abnormal screen referred to colposcopy attended follow up dictated by colposcopist and referred back to NCSP

- Abnormal screen colposcopy recommended lost to follow up/colposcopy declined
- Abnormal screen follow-up cytology advised but declined/lost to follow up
- Abnormal screen cytology performed follow up in 12 months recommended

This information will be shared with the NCSP (as far as possible in a manner that is suitable to the NCSP) and patients will be discharged to GP practice and NCSP

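### Appendix 4 seeks hrHPV type and cytology proportions for NZ to plan colposcopy workload, but the practice mix is set by design and nothing in the protocol links the crude percentages, least of all referrals per 1000, to the national screening population

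*Protocol*

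**What the plan says.** **Target.** Appendix 4 states the aim "to identify, for NZ patients, the relative proportions of hrHPV type and cytology results in order that estimates of colposcopy workloads can be made" and then discusses the national roll-out.

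**Sample.** Under Practice selection, each of three regions supplies five practices. In Whanganui, "five practices were selected by the Whanganui Leadership Team which represent the 6 iwi in the region", and the protocol adds: "The Whanganui population has a high representation of Māori women and rural practice". In each of the other two regions, "four practices from each region would be selected at random", and "an additional practice in each region would be chosen at random from within practices with a higher than population level of eligible Pacific women enrolled".

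**Outputs.** The Methods section calls the analysis largely descriptive, and the Outcome measures are numbers, percentages and summary times. The primary objectives report HPV positivity and type by demographics. The last block of the Outcome measures breaks all outcomes down by screening history, age band, ethnicity, deprivation and region, but only where numbers permit. Statistical Considerations then says that "outcomes related to colposcopy referral will lack the power for stratification".

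**Referral route.** The Referral to colposcopy section allows Pacific and Māori patients, under-screened patients and those with HPV 16/18 to be referred after a positive hrHPV test without cytology triage.

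**Limit on reading.** The section on Covid 19 restricts interpretation to the populations studied at the time. It nevertheless expects some indication of the proportion referred in the first screening round, to guide resources for the new programme.

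**The concern.** Enriching the sample for Māori, Pacific and rural patients suits the equity aim. It suits a national workload estimate only if the results are carried back to the national mix, and the protocol names no step that does so. For hrHPV positivity and type, the planned breakdown by demographics at least supplies the ingredients. For referrals, the quantity that drives workload, the protocol expects not to have that breakdown.

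Referral is also where the mix can act through the pathway itself. If some groups more often go to colposcopy without cytology, referrals per 1000 depend on how many such patients are in the sample, even when positivity is the same in every group. A crude rate scaled up to NZ would carry that dependence into capacity planning, and its confidence interval would not show it.

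**Working it through.** **1. Practice mix (Practice selection).** Leadership-chosen 5/15 = 33%; random within a high-Pacific stratum 2/15 = 13%; plain random within region 8/15 = 53%.

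**2. The plan's own referral figure (Appendix 4).** Inputs: 7% hrHPV positive; 25% of positives HPV 16/18; of other hrHPV, 45% normal and 35% low-grade cytology, which leaves 20%. Per 1000 screened:
- HPV 16/18: 70 × 0.25 = 17.5 (stated 18).
- Other hrHPV: 70 − 17.5 = 52.5. Low-grade: 52.5 × 0.35 = 18.4 (stated 18). High-grade: 52.5 × 0.20 = 10.5 (stated 8, which would need a share of 8/52.5 = 15%).
- Total: 17.5 + 18.4 + 10.5 = 46.4 (stated 44).

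The stated total is therefore not quite reproduced. That is a separate matter; I use 46.4 below and show the effect of using 44.

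**3. Effect of the route at equal positivity.** With triage, 46.4 per 1000 are referred. If every positive goes without triage, 70 are. The rate ratio is RR = 70/46.4 = 1.51. If half do, the rate is (46.4 + 70)/2 = 58.2 and RR = 1.25.

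**4. Effect of the mix.** Let w be the group's national share, s its share of those screened, and suppose everyone else is triaged as planned. Then

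crude rate / national rate = (1 − s + s·RR) / (1 − w + w·RR).

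Practice selection gives national shares of 16.5% Māori and 8.1% Pacific, so w = 24.6% (overlap ignored). The document gives no s; 40-50% is an assumption.

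| Bypass in the group | RR | National per 1000 | Crude, s = 40% | Crude, s = 50% |
|---|---|---|---|---|
| Half | 1.25 | 49.3 | 51.1 (+3.7%) | 52.3 (+6.1%) |
| All | 1.51 | 52.2 | 55.8 (+7.0%) | 58.2 (+11.5%) |
| None | 1.00 | 46.4 | 46.4 (0%) | 46.4 (0%) |

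With 44 instead of 46.4 as the triaged rate, RR at full bypass is 70/44 = 1.59, and the errors are about 4-7% (half) and 8-13% (all).

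Full bypass is a ceiling. Clinician-taken samples receive cytology on the same specimen, and Statistical Considerations expects only 60-70% of patients to self-test.

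**5. Against sampling error.** With 3000 screened and 44 referrals per 1000, the 95% half-width is 1.96 × √(0.044 × 0.956/3000) = 7.3 per 1000, ignoring clustering by practice. The shifts in the table are 1.8 to 3.0 per 1000 (half) and 3.6 to 6.0 (all).

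**6. A case with no shift.** If the seven practices had 40% Māori and Pacific patients and the other eight 10% (assumed), then s = (7 × 0.40 + 8 × 0.10)/15 = 24%, practically equal to w.

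**The case against.** The protocol nowhere says that results will be pooled without weights or scaled to NZ. Standardisation could sit in an analysis plan that is not shown, and hrHPV positivity and type are already to be reported by demographics. The phrase about NZ patients can be read as a contrast with the overseas inputs of Appendix 4, and the Covid 19 section limits the reading. Only Whanganui is purposive, over-representation among those screened is not shown (step 6), and lower uptake in under-served groups would reduce it. Direct referral is permitted rather than required, and it is not confined to ethnicity: it is also allowed where cytology is a barrier or is declined. The plausible shifts lie inside the sampling half-width.

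Much of this stands. It limits the point to a missing link, not a demonstrated bias. It does not remove the point: the aim is national, the mix is set by design, and for referrals the protocol itself gives up the breakdown that would let a reader adjust. Unlike sampling error, a shift from the mix does not shrink with more patients from the same practices.

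A reader might infer more, for instance by setting 10% positivity in the seven practices against 5% in the other eight. The crude figure would be (7 × 10% + 8 × 5%)/15 = 7.3%, against 6.0-6.5% nationally if the group were 20-30% of the eligible population, an error of 13-22%. The document does not support that. Its 5-10% range expresses uncertainty about one overall rate, not a contrast between practices, and a share of practices is not a share of patients.

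**Conclusion.** The concern holds in a limited form. The national workload aim in Appendix 4 is not reconciled with the sampling in Practice selection, with the crude outputs, or with the limit on interpretation in the Covid 19 section. Referrals per 1000 are the weakest point.

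The size and direction of any error cannot be derived from the protocol. The illustration of about 4-6% (half bypass) to 7-12% (full bypass) rests on equal positivity in all groups, a national share of 24.6%, an assumed sample share of 40-50%, equal screening of both groups apart from the route, and the Appendix 4 inputs. Real differences in positivity or type could add to it or offset it. It is zero if the sample share equals the national share or the rates do not differ. The protocol therefore does not support saying that the national estimate will be biased upwards, or that the whole sample is purposive. What it supports is a cheap improvement, not a fault that invalidates the study.

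**What to change.** - Beside the crude figures, report hrHPV positivity, type mix, cytology result and colposcopy referrals per 1000, directly standardised by age band and ethnicity to the NCSP-eligible population.
- Collapse cells in advance. Five age bands by four ethnic groups is 20 cells, and 3000 × 0.044 = 132 referrals is under seven per cell on average.
- Base national workload projections on the standardised figures, with the stated caveat that rurality, deprivation, screening history and the choice of three regions are not corrected. Label the crude figures as describing the study practices.
- Report the age and ethnic mix of those screened beside the national mix, so that the actual over-representation, if any, can be seen.
- Reconcile the aim in Appendix 4 with the limit in the Covid 19 section, either by naming the standardised estimate as the link or by restricting the aim to the practices studied.

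The cost is a small extra analysis and a somewhat wider interval. Age and ethnicity are already collected; population counts would have to come from the NCSP, which funds the study. No extra patients are needed.
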